Of all the possible strategies, the most evaluated to date is annual or biennial FOBT screening. Several randomised controlled trials have shown that FOBT screening with a chemical test (guaiac) reduced mortality from CRC by approximately 15-30% (13-15) and also reduced its incidence (16). However, this method has been disputed because of its low sensitivity, with a detection rate of 30-50% in a single round of screening for CRC (15,17), and of less than 20% for advanced adenoma (18,19). Other disadvantages of screening with the guaiac-based FOBT method are that it needs to be repeated every 1-2 years, that it requires dietary restrictions to ensure the reliability of the test, and that three consecutive samples must be collected, thereby greatly reducing compliance. On the other hand, there are faecal immunochemical tests (FIT) that are more sensitive than chemical methods (20). Such methods specifically detect human haemoglobin, and therefore do not require dietary restrictions and only need a single sample to be taken. However, they have been insufficiently tested in Western countries, and there are no studies on the cost-effectiveness of CRC screening using this procedure.

In the past 15 years several pilot studies have been carried out in Spain for early detection of CRC in average-risk populations (21-25). Most of them used the chemical FOBT method as a screening test, followed by colonoscopy in individuals with a positive result. In total, these studies included more than 12,000 participants, with an average participation rate of 56% and an average detection rate of early stage CRC of 80%. Although these studies are not comparable from the methodological point of view, and were performed at different times, the results suggest an acceptable level of participation in the Spanish population, and high efficacy in the early detection of CRC. However, no studies have been conducted in Spain assessing the efficacy of screening in terms of mortality or incidence over the long-term.

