Colonoscopy is the most accurate method that exists for the early detection and prevention of CRC. Although studies evaluating the effect of screening with this test on CRC-caused mortality in average-risk populations have not yet been published, its implementation is recommended based on the following evidence: 1) studies have demonstrated that colonoscopy with polypectomy reduces the incidence of CRC by 40-90% (27,28); 2) At least two case-control studies suggest that screening by flexible sigmoidoscopy significantly reduces the risk of death from distal CRC (29,30), an effect that lasts for more than 5 years (30) which has enabled extrapolation of its effectiveness to colonoscopy; 3) The prevalence of adenomas in cross-sectional studies of screening by colonoscopy is twice that observed for sigmoidoscopy (18,19,31,32), with colonoscopy also found to be more sensitive than the barium enema or virtual colonoscopy for detecting polyps and CRC (26); 4) Approximately two out of three patients with advanced cancers of the proximal colon do not show neoplasia distal to the splenic flexure, meaning that it would not be detectable in screening by sigmoidoscopy (33,34). This is particularly relevant if one considers that 40% of CRCs are located proximal to the splenic flexure (35).

An additional benefit of colonoscopy every 10 years compared to other screening strategies in an average-risk population is that it allows a long period of protection, which can help improve compliance in the population. It also facilitates diagnosis and treatment in one session, which decreases the risk of the loss of patients to follow-up that occurs with tests that are purely diagnostic.

The primary limiting factors for the use of colonoscopy in screening an average-risk population are its invasive nature, including a possible risk of potentially serious complications such as perforation or post-polypectomy bleeding (1-2 per 2,000 examinations), and a higher cost than other screening methods such as the FOBT test.

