#### 4.4. Study groups, randomisation, and stratification

Asymptomatic men and women aged 50 to 69 years from each participating Autonomous Region will be identified through the corresponding Community Health Registry (CHR) for enrolment into this study. Randomisation will be carried out prior to invitation, with computer-generated lists in blocks of 4 (block randomisation) from the list of health cards, after having previously grouped individuals by household (specified by street address, floor, and apartment number) (see Processes of selecting and inviting the population to be screened section).

All eligible patients will be randomised (1:1 ratio) to the two study groups:

Group 1: Screening by biennial FIT (latex agglutination, OC-Sensor®, cut-off point: 75 ng Hb/ml, corresponding to 15 µg Hb/g of feces), and colonoscopy (after no more than 1 month) for patients with a positive result. Determination of FIT will be made using a single faecal sample, without dietary restriction or interruption of normal treatment of the individual, although the habitual use (>1 month) or recent use (last 7-15 days) of NSAIDs, aspirin, anti-platelet drugs and anticoagulants will be recorded. The above-mentioned cut-off point was used in the baseline round; in subsequent rounds, we decided to modify the cut-off to 20 µg Hb/g of feces since it is the one accepted in the Spanish population-based CRC screening program.

Group 2: Screening by one-time colonoscopy. The ongoing use (>1 month) or recent use (last 7-15 days) of NSAIDs, aspirin, anti-platelet drugs and anticoagulants will also be recorded.

Individuals in Group 1 or Group 2 who do not agree to the type of testing assigned to them may require receiving the alternative test and must still be followed up in order to carry out efficacy analysis according to the intention to screen analysis. The choice of the alternate test will not be actively offered to individuals invited to the study and, accordingly, COLONPREV is not considered a study of sequential screening test offers.

Information on the long-term status of individuals in Group 1 or Group 2 who do not agree to participate in the study will be obtained through population-based registries at the completion of the trial in order to assess efficacy according to the intention to screen analysis.

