#### 4.5. Sample size calculation

##### Considerations for calculation of the sample

Since there are no study examining the effect of screening with the strategies proposed in our trial on CRC-caused mortality, the calculation of the sample in this case must be based on hypothetical studies of cost-effectiveness that analyse the expected reduction in risk of mortality with biennial FIT or colonoscopy every 10 years. Furthermore, the calculation should be adjusted, when possible, to the local conditions where the strategies are to be implemented. In that sense, it is important to note that no study on this subject have yet been published in Spain.

Recently, the Evaluation and Planning Unit of the Canary Islands Health Service has conducted a study of this type based on real data for sensitivity and specificity of the tests in our setting. For a hypothetical population of 100,000 asymptomatic individuals aged 50, the estimated mortality reduction brought about by FIT is 51% and involves a cost of € 2,101/QALY. For the strategy of colonoscopy, the estimate is a reduction in mortality of 75% at a cost of € 2,188/QALY.

With an alpha risk of 0.025 and a beta risk of 0.10 using one-sided test of proportions, 27,749 subjects are required in each arm of the clinical trial (total: 55,498) accepting a non-inferiority condition if the absolute difference was below 1.6% in the CRC-specific mortality rate at 10 years according to the intention to screen analysis and with an expected overall compliance of 30%.

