#### Secondary end points:

1. *Participation, detection rate, diagnostic yield and complication rate at the completion of the first round and at the end of study (10 years)*

Definitions of these four key outcomes are as follows:

- Participation: number of participating individuals (i.e. individuals who completed colonoscopy in the colonoscopy group and individuals who returned the test in the FIT arm) relative to the number of eligible individuals.
- Detection rate: number of true positives relative to the number of participating individuals.
- Diagnostic yield: number of true positives relative to the number of eligible individuals.
- Complication rate: number of major complications (i.e. perforation, postpolypectomy bleeding requiring hospitalization, and cardiovascular/pulmonary complications requiring medical management) relative to the number of participating individuals.

Differences in these four key outcomes between both strategies will be established by logistic regression analysis, adjusted by age, gender and participating centre, and reported as odds ratios (OR) with 95% CI.

*2. Overall survival at the end of study (10 years)*

*3. CRC incidence at the end of study (10 years and 15 years)*

*4. Cost-effectiveness analysis*

Cost-effectiveness will be studied with a Markov's model at the completion of study. Results will be reported in terms of quality-adjusted life years (QALY).

*5. Analysis of factors influencing participation in the study*

Factors associated with participation at the completion of first round and at the end of study (10 years) in each screening strategies will be analysed by logistic regression analysis and results reported as OR with 95% CI. Parameters analysed will include demographics, personal and familial characteristics, socio-economic status, etc.

*6. Number needed to screen to detect a colorectal cancer*

The number needed to screen to detect a CRC will be calculated using the inverse of risk (i.e. the number of participants receiving a given screening modality divided by the number of positive cases in that given modality), with 95% CI computed using the inverse of the binomial standard approximation.

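### The adjusted logistic model planned for major complications may give no finite odds ratio at round one, because the FIT arm could well have no event

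*Combined protocol and SAP*

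**What the plan says.** Section 7, Secondary end points, item 1, lists four key outcomes, among them the "complication rate at the completion of the first round and at the end of study (10 years" years). A major complication is a perforation, a bleed after polypectomy that needs admission, or one of the "cardiovascular/pulmonary complications requiring medical management) relative to the number of participating individuals". All four outcomes share one analysis: "Differences in these four key outcomes between both strategies will be established by logistic regression analysis, adjusted by age, gender and participating centre". Results are to be odds ratios with 95% confidence intervals. The section names no interval method, no method for rare events and no rule for an arm without events.

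The figures that bear on the expected counts are elsewhere:

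- Section 4.5: "27,749 subjects are required in each arm of the clinical trial (total: 55,498"), "with an expected overall compliance of 30"%.
- Section 4.4: "All eligible patients will be randomised (1:1 ratio) to the two study groups". In Group 1 only people with a positive FIT go on to colonoscopy, apart from those who ask for the other test.
- Section 2, on the risks of colonoscopy: "perforation or post-polypectomy bleeding (1-2 per 2,000 examinations").
- Section 2, on earlier Spanish pilot studies: "with an average participation rate of 56"%. Section 4.6 mentions 60% for the trial whose selection process is followed.

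**The concern.** One model is prescribed for outcomes of very different frequency. Participation at 30% means thousands of events per arm. Major complications arise almost only from colonoscopy, they are rare per examination, and most FIT participants never have one. If the FIT arm has no complication, the maximum-likelihood odds ratio is infinite (or zero, depending on the reference arm), and an ordinary interval around it is uninformative.

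Section 2 gives serious complications as a main limitation of screening colonoscopy, and section 3.2 makes their rate a secondary objective at the first round and at 10 years. If the planned method fails, a substitute has to be chosen after the safety counts are known. An odds ratio alone also does not show the absolute excess per 1,000 people screened, which is what a screening programme needs.

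**Working it through.** The plan gives no expected number of complications, so there is no figure of its own to reproduce. Its arm size is used only as the planned number invited (2 × 27,749 = 55,498, as stated).

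**Participants.** 27,749 × 0.30 = 8,325 per arm. This treats the overall 30% as round-one participation, equal in both arms.

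**Group 2.** At 1-2 per 2,000 examinations: 8,325 × 0.0005 = 4.2 to 8,325 × 0.001 = 8.3 events.

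**FIT positivity.** This is not stated, so 5-10% is assumed. A cross-check uses section 2 (sensitivity 57%, specificity 95% for advanced adenoma or CRC, with a different kit) and section 4.8 (5-7% yield of screening colonoscopy, read here as prevalence):

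- prevalence 5%: 0.57 × 0.05 + 0.05 × 0.95 = 7.6%
- prevalence 7%: 0.57 × 0.07 + 0.05 × 0.93 = 8.6%

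**Group 1.** Expected events = 8,325 × positivity × rate, and P(none) = exp(−expected events).

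| Positivity | Rate | Group 1 events | Both arms | P(none in Group 1) |
|---|---|---|---|---|
| 5% | 1/2,000 | 0.21 | 4.4 | 81% |
| 7.6% | 1/2,000 | 0.32 | 4.5 | 73% |
| 8.6% | 2/2,000 | 0.72 | 9.0 | 49% |
| 10% | 2/2,000 | 0.83 | 9.2 | 43% |

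**Sensitivity of P(none in Group 1) at round one**

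- Complication rate doubled, 30% participation, 5-10% positivity: 19-66%.
- Participation 56-60%, rate not doubled, 5-10% positivity: 19-68%, with about 8-18 events in total.
- Both together at 7.6-8.6% positivity: 24-31% from the lower background rate and 6-9% from the upper one. For example, 16,649 × 0.0864 × 0.002 = 2.88 events, and exp(−2.88) = 6%.

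**Model size.** Arm, age (one linear term), gender and seven terms for eight regions make ten parameters besides the intercept. Events per parameter are 4.4/10 to 9.2/10, about 0.4-0.9. Using individual centres would lower this.

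**Regions without events.** With 6 v 1 events, 1,040 participants per arm in each of eight regions and no event in four of them, the region-adjusted model still gives a finite odds ratio of 6.0 (95% CI 0.7 to 50). Only the coefficients of the empty regions diverge.

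**Ten years.** Five FIT rounds at constant participation and positivity give 5 × 0.21 = 1.0 to 5 × 0.83 = 4.2 Group 1 events, so P(none) is 35% down to 2%. Surveillance colonoscopies (section 5) would add events. The end of invitations at age 69 (section 5) and the higher FIT cut-off after baseline (section 4.4) would reduce them.

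**The case against.** The strongest reply is that the inputs lean towards few events, and much of it stands.

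- FIT positivity is an assumption. The cross-check relies on another kit and on reading a yield as a prevalence.
- The background complication rate names perforation and bleeding only, whereas the end point also counts cardiovascular and pulmonary events.
- Section 4.8 says that over half of colonoscopies after a positive FIT involve a therapeutic procedure, so their risk may exceed that of a primary screening examination.
- The 30% is an overall figure, and participation of 56-60% is cited elsewhere.
- Permitted cross-over would add colonoscopies to Group 1 in a comparison by randomised arm.

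So 4-9 events is nearer a floor and 43-81% nearer a ceiling. A reader might infer that the plan's own figures show the analysis will probably fail. They do not: a central input is missing from the documents, and under reasonable alternatives the probability falls well below one half.

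A reader might also infer that regions without events make the treatment odds ratio inestimable. They do not, as the 6 v 1 example shows. Nor does the plan prescribe a Wald interval: it says only 95% CI, and a profile-likelihood, penalised or exact interval would fit that wording. Finally, absolute rates by arm can be derived from the end point's definition, so preferring a risk difference is partly a reporting choice.

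What remains is that the named model has a substantial chance of giving no finite estimate on a stated safety objective, with no alternative specified. The plan should not depend on several favourable assumptions holding together.

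**Conclusion.** The point holds in a limited form, as a cheap improvement. At 30% compliance, the background complication rate and an assumed positivity of 5-10%, the round-one odds ratio is not finite with probability 43-81% (49-73% at 7.6-8.6% positivity). Higher complication rates or participation reduce this to about 19-68% when varied one at a time, and to 6-31% when combined at 7.6-8.6% positivity.

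The exposure is mainly at round one. It would go too far to call the 10-year comparison unworkable, since P(none) there is roughly 2-35% before surveillance colonoscopies. Participation, detection rate and diagnostic yield are not affected, and neither is the primary end point.

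**What to change.** In section 7, Secondary end points, item 1, take the complication rate out of the shared sentence and give it its own:

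- Main comparison at both time points: the difference in risk per 1,000 participants, with a Miettinen-Nurminen (score) or exact 95% interval, and the counts and denominators by arm.
- If an odds ratio is also reported: Firth-penalised or exact logistic regression with arm as the only term.
- Adjusted logistic regression stays for participation, detection rate and diagnostic yield.

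The risk difference can be estimated with an empty arm. For illustration, 6 v 0 events among 8,325 per arm gives 6/8,325 = 0.72 per 1,000, with a Miettinen-Nurminen 95% interval of 0.26 to 1.57.

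The cost is one SAP sentence and the loss of adjustment for age, gender and centre in this comparison, which so few events could not support. Section 8 schedules the first-round analysis for July 2011. If that comparison has already been made, the new method should be labelled as added afterwards for round one.

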#### **3.2. Secondary objectives**

- To compare diagnostic yield and detection rate of CRC and/or advanced adenomas in each screening strategy at the completion of the first round.
- To compare the participation rate in each screening strategy at the completion of the first round, and identify the factors influencing it (i.e. demographics, personal and familial characteristics, socio-economic status, etc.).
- To compare overall diagnostic yield and detection rate of CRC and/or advanced adenomas in each screening strategy at 10 years.
- To compare the overall adherence rate in each screening strategy at 10 years, and identify the factors influencing it.
- To assess the cost-effectiveness of each screening strategy.
- To assess the rate of serious complications in each screening strategy, both at the completion of the first round and overall at 10 years.
- To compare CRC incidence in each screening strategy at 15 years.

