## 5. DEVELOPMENT OF THE STUDY

This research project is included within the population-based screening programme of each Autonomous Region. This screening programme will ensure the recall of individuals for appointments in successive rounds of screening, while also continuing the strategy assigned to them during the randomisation of the study. The investigators will also be responsible to electronically or manually transfer to the LSO the information derived from the study that is of interest to the population screening programme.

Each Autonomous Region is committed with recruiting the same number of individuals regardless of the number of participating health centres or hospitals in each region.

The dynamics of the study are summarised as follow:

- Participants in Group 1 with a negative FIT will remain in their assigned group and will be offered the next round of screening at 2-year intervals until the age of 69. All of them will be sent a letter informing them of the test result and the date of the next round of screening. Individuals who enter the study at the age of 68 or 69 will undergo a single round of screening.
- Participants in Group 1 with a positive FIT will be contacted by phone and sent a letter informing them of the test result and the date of their appointment with the primary care physician (or specialist) or the person responsible for the screening programme, depending on the Autonomous Region. They may be assisted in this task by the project staff. During the visit they will be informed about the colonoscopy procedure and will be scheduled for this procedure.
- Participants in Group 1 with a positive FIT but who have normal colonoscopies or in whom only non-neoplastic disease is detected will remain in the FIT arm and will be offered the next round of screening using the biennial FOBT test at 10 years after performance of the colonoscopy.
- Participants in Group 2 who are found to be negative in colonoscopy or in whom only non-neoplastic disease is detected, will remain in the colonoscopy arm and will be offered a new colonoscopy at 10 years after performance of the baseline colonoscopy.

Surveillance colonoscopy for patients with adenomas will be carried out according to the Joint Guideline from the *US Multi-Society Task Force (USMTF)* (45).

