### Intention-to-treat

Cumulative incidence curves for the invitation arms will be estimated with the Kaplan-Meier estimator, considering the period from the day of randomization to the end of follow-up. The Kaplan-Meier estimator with daily outcome events will be used to compute the probability (risk) of the outcome during the period. For CRC incidence and mortality, non-CRC events will be considered as censoring events. We will calculate the 10-year risk differences and risk ratios between the trial arms, whereas 95% confidence intervals (95% CI) will be computed using the normal approximation.

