## 8. CHRONOGRAM

The study will be developed according to the following chronogram:

- Initial meeting: October 28th, 2008
- Formative meeting for data-collectors and other auxiliary staff: December 12th, 2008
- Informative campaign launched by the Spanish Alliance for CRC Prevention and involving national and local media: from November 2008 to March 2009
- Recruitment period will be initiated in June 2009
- Quality Committee meetings will be held during the first round according to the following calendar:
  - June 12th, 2009
  - December 11th, 2009
  - June 11th, 2010
  - December 10th, 2010
- First round of screening will be finished in June 2011
- First follow-up meeting (first-round interim analysis): July 2011
- Other follow-up meetings will be held regularly during the study period, in a biennial basis (date will be announced properly)
- Other Quality Committee meetings will be held regularly during the study period, in a annual basis (date will be announced properly)
- Completion of the study: December 2021
- Analyses of main end point results (i.e. CRC mortality and incidence and any-cause mortality at 10 years): June 2024
- Follow-up conference calls among members of the Executive Committee will be held periodically, every four months, during the study period.

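### CRC incidence at 15 years is set as an end-of-study end point, but at study completion nobody has more than about 12.6 years of follow-up, and no later data cut, linkage or analysis is scheduled

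*Combined protocol and SAP*

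**What the plan says.** Section 3.2 lists, as a secondary objective, "To compare CRC incidence in each screening strategy at 15 years". It gives no calendar date for this. Section 7, under the secondary end points, turns it into item 3, "CRC incidence at the end of study (10 years and 15 years", so that both horizons fall at the end of study. Items 1, 2 and 5 of the same list equate the end of study, or the final time point, with 10 years.

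The chronogram (section 8) gives four relevant dates:

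- "Recruitment period will be initiated in June 2009"
- "First round of screening will be finished in June 2011"
- "Completion of the study: December 2021"
- "Analyses of main end point results (i.e. CRC mortality and incidence and any-cause mortality at 10 years): June 2024"

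In the SAP, the intention-to-treat, as-screened and per-protocol analyses all use the Kaplan-Meier estimator, "considering the period from the day of randomization to the end of follow-up". Each then calculates risk differences and risk ratios at 10 years, and at no other horizon. Section 4.4 says that the long-term status of people who decline to take part will be taken from population-based registries when the trial is completed. It mentions no later linkage.

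**The concern.** A Kaplan-Meier curve gives no risk beyond the longest observed follow-up time. If the data stop at study completion and nobody has been followed for 15 years by then, the 15-year end point has no estimate in either arm. More people or more events would not change that.

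At stake is a listed secondary objective. If the plan stays as it is, four things could happen:

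- the end point is dropped without comment;
- it is extrapolated;
- it is read off a curve whose tail rests on very few people;
- a follow-up extension is chosen after the 10-year results are known.

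The last two are the more damaging, because the cut-off and the method would then be open to choice by people who have already seen the comparison.

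**Working it through.** **Inputs.** Start of recruitment June 2009, end of first round June 2011, completion December 2021 and main analysis June 2024, all from section 8. Time origin is the day of randomisation (section 7). The chronogram gives months only, so the first or last day of the month is used as stated. Years are days / 365.25.

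**Formula.** Follow-up = data cut-off minus date of randomisation.

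**Step 1: the plan's own 10-year horizon.** If the last entry is 30 June 2011 (an assumption; the documents date the end of the round, not the last randomisation), follow-up to 31 December 2021 is 10.51 years. Everyone entered by then passes 10 years, so the 10-year horizon fits the schedule.

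**Step 2: the 15-year horizon at completion.** The earliest entrant, on 1 June 2009, has 12.58 years by 31 December 2021. The shortfall is 15 − 12.58 = 2.42 years for the earliest entrant, and 15 − 10.51 = 4.49 years for an entrant on 30 June 2011. The share reaching 15 years is 0%.

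**Step 3: could earlier randomisation rescue it?** Randomisation precedes invitation, so some people may have been randomised before June 2009.

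| Earliest randomisation | Follow-up to 31 December 2021 |
|---|---|
| 1 June 2009 (recruitment opens) | 12.58 years |
| 13 April 2009 (7 weeks earlier: the 4 weeks between letters in section 5.1 plus the 3-week lag in section 4.6) | 12.72 years |
| 28 October 2008 (initial meeting, an extreme case) | 13.17 years |

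None reaches 15 years. This step does not depend on when entry ended.

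**Step 4: what if data ran to the June 2024 analysis?** With entry from 1 June 2009 to 30 June 2011, follow-up to 30 June 2024 runs from 13.0 to 15.08 years. Reaching 15 years requires randomisation by 30 June 2009. With uniform entry (an assumption), that is 29 of 759 days, about 4%.

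The share depends on the assumed entry window:

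- Entry starting 7 weeks earlier: (49 + 29) / (49 + 759) = 78 / 808, about 10%.
- As above, and also ending six months earlier, on 31 December 2010: 78 / (49 + 578) = 78 / 627, about 12%.

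In each case only the earliest entrants contribute at 15 years.

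**Step 5: when would everyone reach 15 years?** June 2011 + 15 years = June 2026, if entry had ended by June 2011.

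**The case against.** The strongest reply is that section 3.2 does not tie the 15-year comparison to the end of study, and that the June 2024 entry in the chronogram is confined to 10-year results. A later registry-based analysis at 15 years is compatible with both, and may be what is intended. On this reading the conflict lies in one line of the end-point list. This stands in part: the end point is not impossible in principle. But no section gives a data cut, a linkage or an analysis date for it, and no SAP analysis defines a 15-year estimate. As written, the schedule cannot deliver it.

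A second reply concerns the dates. The documents do not say when the last person was randomised. Randomisation precedes invitation, and the first round includes reminders at 3-4 months and again 2 months later, so entry may have ended well before June 2011. In the other direction, section 4.3 lets temporarily excluded people enter later, without saying how their start date is set. This stands for the 10.51-year and June 2026 figures, which are conditional. It does not touch the 12.6-year maximum.

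A reader might also infer two stronger points, which the documents do not support.

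- *That cancers found at the 10-year offer would enter the colonoscopy arm only.* Section 5 says that Group 2 participants with a negative examination "will be offered a new colonoscopy at 10 years after performance of the baseline colonoscopy". The same list gives Group 1 later screening too: biennial rounds up to age 69 after a negative FIT, and a renewed offer 10 years after a positive FIT with a normal colonoscopy. Adenoma surveillance runs in both groups. Timing and intensity may differ between arms, but later detection is not confined to one.
- *That a 15-year comparison is no longer the contrast named in the objective.* The 15-year objective speaks only of each screening strategy. The one-time label belongs to the primary objective, which is set at 10 years, and to the description of Group 2. An intention-to-screen comparison at 15 years can properly compare the strategies as delivered. What remains is a labelling ambiguity between one-time colonoscopy and the 10-year offer.

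**Conclusion.** The point holds on timing. On the chronogram's dates, follow-up at completion is at most about 12.6 years (12.7 if randomisation began 7 weeks before recruitment opened, 13.2 in the extreme case). A 15-year Kaplan-Meier risk therefore cannot be estimated at the end of study as item 3 requires. The plan schedules no later cut-off, linkage or analysis that would supply it.

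The maximum rests only on the stated start and completion dates. The 4% share at June 2024 rests on assumed uniform entry from June 2009 to June 2011. June 2026 rests on entry having ended by June 2011.

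The consequence is limited to one secondary objective and end point. The primary end point, 10-year incidence and the sample size are unaffected. The change should be made, because it is cheap and decides whether a listed objective can be answered.

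**What to change.** 1. In section 7, secondary end points, item 3, limit the end-of-study incidence end point to 10 years.
2. Then choose one of two courses:
   - *Keep 15 years.* List it as a separate end point with its own registry-linkage cut-off for all randomised people. Add the linkage and the analysis to the chronogram, extend the registry statement in section 4.4 to match, and add a 15-year risk difference and risk ratio to the three SAP analyses. Set the cut-off from the actual last randomisation date; if that was no later than June 2011, a cut-off of about June 2026 gives everyone 15 years.
   - *Drop 15 years.* Remove it from section 3.2 and from item 3.
3. If it is kept, state that the 15-year intention-to-screen contrast compares the strategies as delivered, including screening offered at or after 10 years in both groups. Reconcile the one-time colonoscopy label with the 10-year offer in section 5. Which wording is right is for the investigators to decide.

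Replacing 15 years with the longest horizon that everyone reaches by December 2021 is not worthwhile. It would nearly duplicate the 10-year end point and would rest on an unstated entry date.

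The cost is wording in sections 3.2, 4.4, 5, 7 and 8, plus one later registry linkage if 15 years is kept.
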